1.2 SCHEMA

1.3 SCHEDULE OF ACTIVITIES

Timeline	Year 1				Year 2				Year 3				Year 4				Year 5			
	Q1	Q2	Q3	Q4	Q1	Q2	Q3	Q4	Q1	Q2	Q3	Q4	Q1	Q2	Q3	Q4	Q1	Q2	Q3	Q4
R61 Planning Phase																				
R33 Implementation Phase																				
Identification of cohort #1					X															
Randomization #1					X															
Mailing of Intervention Materials							X													
Blackout period								X												
6-month observation period									X	X										
Primary and Secondary Outcome ascertainment											X	X								
Statistical analysis of 1st mailing													X							
Meeting with DSMB													X							
Implementation Phase 2																				
Identify Study Cohort #2													X							
Randomization #2													X							
Mailing of Intervention Materials														X						
Blackout period															X					
6-month observation period																X	X			
Primary and Secondary Outcome ascertainment																		X	X	
Analysis of 2nd Mailing																				X
Meet with DSMB		X	X			X		X	X	X	X	X		X	X	X	X	X	X	X
Prepare manuscript													Ongoing							
Dissemination																	X	X	X	X
Engagement with stakeholders and advisors													Throughout the study							

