5.1 INCLUSION CRITERIA

Eligibility criteria: To be eligible for enrollment in the study, the following inclusion criteria will be met: a) diagnosis of AD/ADRD based on the Chronic Conditions Data Warehouse codes, or treatment with a pharmacologic therapy used for AD (e.g., donepezil, rivastigmine, galantamine, and memantine) in the 365 days prior to or on cohort entry date. (N.B. The two AD/ADRD ICD-10 diagnosis codes must be ≥ 7 day apart and at least one of the codes must be within 365 days of the cohort entry date. Treatment is defined as exposure to an AD drug based on either: (1) days' supply of one or more dispensing; or (2) a dispensing in the 365 days prior to cohort entry date.) (b) evidence of inappropriate prescribing within the 3 months prior to cohort entry date; (c) age ≥ 50 years of age as of cohort entry date; and (d) continuous medical and pharmacy insurance coverage for at least the prior year.

Exclusion Criteria:

An individual who meets any of the following criteria will be excluded from participation in this study:

1. Evidence of a recent institutional stay encounter in a Skilled Nursing Facility, hospice, rehab center, nursing home, residential, overnight non-hospital dialysis and other non-hospital stays within the previous 90 days prior to or on cohort entry date.
2. Incomplete/missing prescriber ID or incomplete contact information for either patient or prescribing provider.
3. On “do not contact” list

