9.4.2 ANALYSIS OF THE PRIMARY ENDPOINT(S)

PRIMARY OUTCOME

Statistical Analysis of Primary Outcome:

1. The primary outcome will be defined as absence of any dispensing of the targeted inappropriate prescription class from day 91 to day 270 following the day of mailing. Educational interventions will be targeted towards one specific drug class so participants who switch within one class (e.g. clonazepam to lorazepam) will not be considered as having met primary outcome. **The intervention will only target one potentially inappropriate medication class for patients who are on more than one class of potentially inappropriate medication.**
2. **Timing of Ascertainment:** The timing of ascertainment is over a 6-month period beginning 3 months after mailing/intervention – i.e., we will assess evidence of a dispensing in days 91 through 270 after the date of mailing.
3. **Method of Aggregation: Hazard ratio.** The data on primary outcome will be measured as the relative hazard of time to dispensing of any new incident inappropriate prescription of

their initial drug class in the intervention vs control group. The index date for the survival analysis will be Day 91 for the trial. We chose the hazard ratio as method of aggregation as this allows the statistical analysis to account for censoring due to death or disenrollment.

4. Any prescriptions dispensed during the **blackout period** will not be counted towards measurement of the primary outcome but may affect subsequent dispensing. In covariate-adjusted survival analyses, we will adjust for whether any prescription for the same inappropriate medication class was dispensed during the blackout period and the duration of such dispensing because dispensing during the blackout period is an important factor which may affect the primary outcome. A blackout period was needed to allow time for the mailing and receipt of the intervention after randomization, and the opportunity to set up the appointment with or contact their provider to discuss the use of the potentially inappropriate medication. Alternatively, we may also consider stratification of survival analyses by prescriptions dispensed during the blackout period.

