Measurement of Dose Reduction. We will consider dose reduction for each selected drug as being a $\geq 50\%$ decrease in the mean daily dose comparing the 6 months immediately prior to the randomization with the 6-month study window period. (day 91-day 270). We will measure average daily dose using dates of prescription dispensing, duration of prescription dispensing and strength of the prescription. We will measure the dose reduction as a dichotomous variable defined as the proportion of patients who achieved a more than 50% dose reduction in the daily dose during the study window period (day 91 to day 270) compared to the 6-month period prior to randomization. Measurement of dose reduction over 6 month follow-up requires participants to complete follow-up through end of observation period (day 270). Censored participants – that is, those who have less than 6 months in days 91-270 – will be excluded for the analysis of dose reduction. Analyses will adjust for correlates of missing data. Analyses for post-intervention polypharmacy prevalence will be analogous. We will identify participants with evidence of dispensings of ≥ 5 oral medications over the respective 6-month periods [during the study window period (day 91 to day 270) compared to the 6-month period prior to mailing]. AD medications and the three potentially inappropriate medication classes will contribute to measure of polypharmacy. Injectables and topical or ocular medications will not be counted as evidence of polypharmacy.

A combination drug will be considered a single medication for the purpose of this analysis. Additional analyses will examine within-patient change in number of inappropriate medications, where the maximum possible decrease equals the pre-intervention number of inappropriate medications. We will accommodate this between-patient heterogeneity as follows: within-patient changes will be ranked separately by pre-intervention number of inappropriate medications, ranks will be transformed using normal scores to obtain comparable distributions across these strata, and treatment arms will be compared regarding transformed ranks³⁴ using analysis of covariance. In analyses of other secondary outcomes, count outcomes such as per-patient number of emergency department (ED) visits will be analyzed using Poisson or negative binomial regression, accounting for “excess” zeros if warranted based on observed distributions.³⁵

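### The dose-reduction baseline ends at randomisation while the polypharmacy baseline and day 0 are tied to mailing, so dose cuts made before any letter was mailed count as responses in every arm

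*Combined protocol and SAP*

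**What the plan says.** Under Measurement of Dose Reduction, section 9.4.3 sets the comparison as "comparing the 6 months immediately prior to the randomization with the 6-month study window period". It repeats the anchor when it defines the dichotomous outcome, which is judged "compared to the 6-month period prior to randomization". The same section calls the polypharmacy analysis analogous but defines it "during the study window period (day 91 to day 270) compared to the 6-month period prior to mailing".

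The follow-up window counts from mailing. Section 9.4.2 states that "we will assess evidence of a dispensing in days 91 through 270 after the date of mailing", and section 9.4.3 uses the same window for the secondary outcomes.

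In section 1.3, "Randomization #1" is marked in Year 2 Q1 and the first "Mailing of Intervention Materials" row in Year 2 Q3. Blackout and observation follow in order, in Year 2 Q4 and Year 3 Q1-Q2. For the second trial, randomisation is in Year 4 Q1 and mailing in Year 4 Q2.

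The only prescription-related covariate that sections 9.4.1 and 9.4.2 name is dispensing in the blackout period, which comes after mailing. Nothing in section 9.4.3 explains the two anchors or deals with dose changes between randomisation and mailing.

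**The concern.** Section 3 gives the reason for this endpoint: some target drugs need a gradual taper, so the intervention may show only as a lower dose. The endpoint should therefore measure change from the regimen in force when the letter went out. As written, it measures change from a regimen that ended when the patient was randomised. A cut made between the two dates is scored in the same way as one prompted by the letter, including in usual care.

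Three things are at stake: the size of the arm-level response percentages, the power of the between-arm comparison on this secondary endpoint, and whether the dose and polypharmacy changes describe the same period. The primary outcome uses no baseline dose and is unaffected.

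**Working it through.** **1. The plan's own power figure.** Section 9.2 gives 4814 per arm, 9.9% lost by day 90, 13.5% censored in days 91-270, two-sided alpha 0.05/3 = 0.0167 and 80% power. Then 4814 × 0.901 = 4337 per arm. At 75% failure and a hazard ratio of 0.9165, Arm 2 failure is 1 - 0.25^0.9165 = 0.7193. Expected events are 2 × 4337 × 0.865 × (0.75 + 0.7193)/2 = 5513. The Schoenfeld formula needs 5509, so power is 80.0%. The stated 0.9165 reproduces, and the power arithmetic is not at fault. Section 9.2 says the dose-reduction calculations are parallel and gives no separate figure.

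**2. Length of the gap.** Quarter columns are coarse.
- First trial, Year 2 Q1 to Q3: from 3 months (end of Q1 to start of Q3) to 9 months (start of Q1 to end of Q3).
- Second trial, adjacent quarters: from 0 to 6 months.

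**3. The two baselines side by side (months relative to mailing).**

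| Gap | Randomisation baseline | Mailing baseline | Overlap | End of randomisation baseline to day 91 |
|---|---|---|---|---|
| 3 | -9 to -3 | -6 to 0 | 3 months | 6 months |
| 6 | -12 to -6 | -6 to 0 | none | 9 months |
| 9 | -15 to -9 | -6 to 0 | none | 12 months |

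**4. A halving in the gap.** Take a patient continuously supplied at dose D before randomisation, halved before mailing and unchanged after that.
- Randomisation baseline: 0.5D / D = 0.50, a response under the ≥50% rule.
- Mailing baseline with m of its six months at full dose: the mean is D(6 + m)/12, so the ratio is 0.5D divided by this, or 6/(6 + m).
- With a 6-month gap, a halving 0 to 5 months after randomisation gives m = 0 to 5 and ratios from 1.00 to 0.55, so no response. The ratio reaches 0.50 only if the halving falls at mailing.
- With a 3-month gap, a halving 0 to 2 months after randomisation gives m = 3 to 5 and ratios from 0.67 to 0.55, again no response.

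One sentence of section 9.4.3 says more than 50% instead of ≥50%. On that wording an exact halving fails, but any slightly larger cut behaves as above.

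**5. Dilution.** Let g be the share of every arm that has already qualified by mailing and stays so, and let p be the response probability in the rest. Each arm's response is g + (1 - g)p, so the difference is (1 - g)(p_T - p_C). If p_T = p_C the difference is zero for any g, so the null is preserved.

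Section 9.4.3 restricts this analysis to patients followed through day 270: 4337 × 0.865 = 3752 per arm. The two-proportion power at two-sided alpha 0.0167, starting from a difference detectable with 80% power, is as follows. Both g and the control rates are assumptions.

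| g | Control 25.0% vs 28.3% | Control 10.0% vs 12.35% |
|---|---|---|
| 0 | 80% | 80% |
| 5% | 71% | 61% |
| 10% | 63% | 46% |
| 20% | 47% | 28% |

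**The case against.** **Randomisation is a legitimate baseline.** Section 9.4.5 takes descriptive baseline characteristics from claims at randomisation, so polypharmacy could be called the odd one out and moved instead. This stands as a reason why the choice is not self-evident. It does not remove the problem: section 9.4.5 concerns descriptive tables, and follow-up is counted from mailing. No arm is treated differently before mailing, so a mailing baseline is equally free of treatment effect if usual care gets the same index date.

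**The two dates may nearly coincide.** Section 9.4.2 says the blackout allows time for mailing and receipt after randomisation, which suggests a short gap. The schedule shows two quarters. If the gap proved short, little would change under either anchor.

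**The size is unknown.** This stands. The documents give no rate of dose change before mailing.

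**Re-anchoring is partial.** This stands too. A patient who stops completely shortly before mailing still has baseline supply and still counts as a response, so less than the full g is recoverable.

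**Recent starters.** Eligibility requires only "evidence of inappropriate prescribing within the 3 months prior to cohort entry date", so a reader might infer that patients who started recently have a mostly empty six-month baseline and that their real reductions would be scored as increases. The documents do not support this. Section 9.4.3 builds mean daily dose from dispensing dates, duration and strength, which is equally compatible with dose per supplied day, and on that reading the distortion does not arise. What remains is that the denominator is not stated.

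**Conclusion.** The point holds. Section 9.4.3 contains two baseline anchors that must be reconciled, and the one used for dose reduction counts cuts made before mailing as responses. The consequence is inflated arm-level percentages and a between-arm difference reduced by about (1 - g) on a secondary endpoint. The power losses in the table are illustrations over an assumed range of g, not estimates.

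A reader might infer that the comparison between arms is biased or that false positives rise. Neither follows: changes before mailing fall alike on all randomised arms and the null difference stays zero. Nor should the point be read as saying that no letter existed before the gap; section 4.1 records that materials had been piloted to 200 patients at each plan. What matters is that no trial letter had been mailed to these patients. The two-quarter gap applies to the first trial only.

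**What to change.** In section 9.4.3:

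- Anchor the dose-reduction baseline to the six months before the mailing date (day 0), as is already done for polypharmacy ("compared to the 6-month period prior to mailing"), and assign the same index date to usual care.
- State the denominator for mean daily dose and use the same one in the baseline and follow-up windows, with a complete stop counted as zero dose in follow-up.
- Keep the randomisation-anchored baseline as a sensitivity analysis that retains all randomised completers.
- Report by arm the patients with no target-class supply in the six months before mailing.

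The cost is revised wording and a small change to the claims program, with no new data and no added patients. There are two drawbacks. Patients who stopped well before mailing have no baseline dose and leave the main analysis of this endpoint, which is why the sensitivity analysis and the count by arm are needed. Complete stops shortly before mailing still count as responses, so dilution is reduced but not removed.

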Eligible Study Population and Demographic Characteristics for the Feasibility Analysis. We identified a total of **26,259** trial-eligible members who were living with AD/ADRD and had current evidence of prescribing of antipsychotics, sedative-hypnotics, and strong anticholinergics. This corresponds to approximately 20% of the 130,682 members with AD/ADRD (having diagnosis codes for AD/ADRD or dispensing's for ADRD drugs). These individuals had a mean age of 78.8 years (SD 9.2); 92% were age 65 or older and 28% were age 85 or older; 68% were women. They had a Charlson Comorbidly Score of 5.1 (SD 3.2). Based on available data on race/ethnicity, we estimate that 82% were White, 15% were Black or African American, 1% were Asian, <1% were Native Hawaiian or Pacific Islander, <1% were American Indian or Alaska Native, and <1% were more than one race. Approximately 3% were Hispanic.

Proportion of AD/ADRD participants with Inappropriate Prescribing. Among members with AD/ADRD (n=130,682) 9.6% were dispensed antipsychotics, 5.1% were dispensed sedative-hypnotics, and 8.6% received strong anticholinergics. These findings which allowed patients to be on multiple inappropriate medication classes are shown (**Table 1 A**)

Table 1A. Characteristics of AD/ADRD Population with current evidence of potentially inappropriate prescribing in Health Plans Jan January 2019-January 2020*	
Number of health plan members with AD/ADRD	130,682
Number of health plan members with AD/ADRD and evidence of potentially inappropriate prescribing N, %	26,259, 20.1%
Antipsychotics N, %	12,581, 9.6%

Sedative hypnotics N, %	6,617, 5.1%
Strong anticholinergics N, %	11,228, 8.6%

**Members could be on multiple classes of medications and so sum of total inappropriate percentage > 20.1%*

Several patients in the study were on more than one class of inappropriate medications. We plan to evaluate the effect of the intervention on a single class of targeted inappropriate prescriptions in the trial. In consultation with our Advisory panel and based on relevance and importance for this study population, for patients who were on multiple medication we will prioritize antipsychotics (9.6%) over sedative-hypnotics (3.9%) and sedative-hypnotics over strong anticholinergics (6.5%) as shown in **Table 1B**. As a result, this analysis displays patients based on this hierarchy.

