9 STATISTICAL CONSIDERATIONS

9.1 STATISTICAL HYPOTHESES

Primary Endpoint:

We hypothesize that, compared to patients in the control group, patients who are in either intervention arm and receive information around inappropriate prescribing themselves along with their provider, or who have a provider that received the mailing, will have reduced inappropriate prescribing. Alternatively, our null hypothesis is that there will be no difference in the effects of the educational intervention at the end of the observation period.

Secondary Endpoint(s):

We hypothesize that education on inappropriate prescribing among patients/caregivers and their providers can reduce medication-related morbidity in patients with AD/ADRD and lead to an improvement

in medication safety for this vulnerable population. This will be measured by assessing evidence of dose reduction of the selected inappropriate medication, reduction in the prevalence of polypharmacy; reduction in the rates of emergency room visits; rates of hospitalizations; rates of non-acute institutional stays (e.g., skilled nursing facilities); overall health care utilization (number of outpatient visits, days hospitalized, emergency department visits, and non-acute institutional days); and in-hospital mortality.

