9.4.3 ANALYSIS OF THE SECONDARY ENDPOINT(S)

Secondary outcomes. These will also be assessed specific to the 6-month observation period (days 91-270 following mailing/intervention) based on health plan claims data including:

- a) Any dose reduction of each of the targeted medications, assessed at the participant level using health claims data (outpatient dispensings).
- b) Percentage of patients with prevalence of polypharmacy (defined as >5 active prescriptions for different oral agents)³²
- c) Rates of emergency room visits; rates of hospitalizations; rates of non-acute institutional stays (e.g., skilled nursing facilities); overall health care utilization (number of outpatient visits, days hospitalized, emergency department visits, and non-acute institutional days).
- d) In-hospital all-cause mortality
- e) Switching within classes

We will use administrative claims data to identify encounters of interest (ED visits, hospitalizations, non-acute institutional stays, outpatient visits) and only assess oral formulations for medications.

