9.4.7 SUB-GROUP ANALYSES

We will conduct analyses stratified by sex and we do not anticipate sex related differences in within- group correlations (ICC). We will also conduct analyses of primary and secondary outcomes stratified by each individual drug class. Pre-specified analyses of primary and secondary outcomes will be conducted according to levels of polypharmacy at baseline (5+ medications at baseline; 7+ medications at baseline).

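### Polypharmacy is analysed only as crossing a threshold, never as the number of oral agents, so most single-drug stops leave the endpoint unchanged; add a baseline-adjusted count.

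*Combined protocol and SAP*

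**What the plan says.** Section 9.1 lists "reduction in the prevalence of polypharmacy" among the measures of the secondary, medication-safety hypothesis. The endpoint list in 9.4.3 reads "Percentage of patients with prevalence of polypharmacy (defined as >5 active prescriptions for different oral agents"), and the synopsis, Section 3 and Section 8.1 use the same cut. The analysis text later in 9.4.3 uses another: "We will identify participants with evidence of dispensings of ≥ 5 oral medications over the respective 6-month periods", comparing days 91-270 with the six months before mailing.

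For the method, 9.4.3 says of dose reduction "We will measure the dose reduction as a dichotomous variable", excludes participants censored before day 270, and continues "Analyses for post-intervention polypharmacy prevalence will be analogous". On what is counted it says "AD medications and the three potentially inappropriate medication classes will contribute to measure of polypharmacy"; non-oral products are left out and a combination product counts once.

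Section 9.4.3 also plans a rank-based analysis of covariance of within-patient change, but in the number of inappropriate medications only. Section 9.4.7 plans subgroups at "5+ medications at baseline; 7+ medications at baseline". No section analyses the number of all oral agents, and none gives its mean, its SD or the share of patients above the cut.

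**The concern.** Sections 4.1, 6.1.2 and 9.4.2 limit the intervention to one class per patient, so a success usually lowers the number of oral agents by about one. A flag registers that only in patients exactly at the cut; someone who goes from nine agents to eight, or from four to three, contributes nothing.

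The flag is also the plan's only measure of whether total medication burden fell. A null on prevalence could be read as no effect on burden, or as stopped drugs being replaced by drugs outside the targeted class, when the measure could hardly have shown a change. The claims program has to count oral agents to set the flag, so the more sensitive measure will already exist.

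**Working it through.** **Inputs from the documents (9.2).** 4,814 patients per arm; 9.9% lost before day 91, leaving 4,337; 13.5% censored in days 91-270; two-sided alpha 0.05/3 = 0.0167; 80% power.

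**Reproducing the plan's own figure.** There is no power statement for polypharmacy, so Table 2 serves as the check on these inputs. Schoenfeld's formula requires 4 × 3.236² / (ln HR)² events, where 3.236 = z(1 − 0.05/6) + z(0.80) = 2.394 + 0.842. At HR 0.9165 that is about 5,510 events. Expected events are 4,337 × 0.865 × (0.75 + 0.7193) ≈ 5,512. Table 2's row for 75% is reproduced. Its Arm 2 failure probability of 0.7193 means 75 − 71.93 = 3.07 points more stopping, used below for scale.

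**Patients available for polypharmacy.** Completers only, as for dose reduction: 4,337 × 0.865 ≈ 3,751 per arm.

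**Assumptions, not in the documents.** Oral agents per six months follow a negative binomial distribution with mean 6, 8, 10 or 12 and SD 3, 3.5, 4 or 4.5. Correlation between baseline and follow-up is 0.7 or 0.85 (specified on an underlying normal scale; the counts correlate about 0.01 lower). Each extra stop removes one agent, regardless of how many the patient takes.

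**Formulas.** With k = 3.236 × √(2/3,751) = 0.0747, the between-arm stopping difference detectable with 80% power is
- count: k × (residual SD of the count given the baseline count);
- flag: k × (residual SD of the flag given the baseline count) / P(exactly at the cut).

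The relative efficiency of the count is the square of the ratio, flag over count.

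**Example: mean 8, SD 3.5, correlation 0.85, cut at ≥5.** Count: residual SD 3.5 × √(1 − 0.842²) = 1.89, so 0.0747 × 1.89 = 14.1 points. Flag: residual SD 0.268 and P(exactly 5) = 0.097, so 0.0747 × 0.268 / 0.097 = 20.6 points. Efficiency (20.6/14.1)² ≈ 2.1.

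**Results, cut at ≥5** (points of stopping difference; the two values are for correlation 0.7 / 0.85):

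| Mean / SD | Above cut | Exactly at cut | Count | Flag | Efficiency | Efficiency, no baseline adjustment |
|---|---|---|---|---|---|---|
| 6 / 3 | 66% | 13.9% | 16 / 12 | 21 / 18 | 1.7 / 2.2 | 1.3 |
| 8 / 3.5 | 85% | 9.7% | 19 / 14 | 24 / 21 | 1.6 / 2.1 | 1.1 |
| 10 / 4 | 93% | 5.5% | 22 / 16 | 30 / 26 | 1.9 / 2.7 | 1.3 |
| 12 / 4.5 | 97% | 2.8% | 24 / 18 | 40 / 36 | 2.7 / about 4 | 1.7 |

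With the cut at >5, 4% to 13% sit exactly at the cut and the adjusted efficiency is 1.6 to 3.1. At mean 5 (SD 3), where 38% to 51% are above the cut depending on its definition, it is still 2.1 to 3.7. The advantage therefore does not need most patients to be above the cut. The flag is treated generously here: adjusted only for its own baseline value, it needs 20 to 41 points.

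**At the plan's effect of 3.07 points.** In the best case for the count (12.2 points needed), power is Φ(0.0307/0.122 × 3.236 − 2.394) = Φ(−1.58) ≈ 6%. Neither measure detects it. The count's interval is still informative: at the 0.0167 level its half-width is (2.394/3.236) × 0.12 to 0.24, about 0.09 to 0.18 agents per patient.

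**At the cited trial's 31 points (2.2).** The count suffices in every row; the flag suffices at means 6 to 10 but not at 12.

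**The case against.** The strongest reply is that little depends on this endpoint. Stopping the targeted class is the primary outcome. Dose reduction, within-class switching and change in the number of inappropriate medications are also planned. What remains unmeasured is net change in all oral agents, on one secondary endpoint, and the count too would miss an effect of the size in Table 2. All of that stands. It limits the importance of the point, but none of the listed analyses shows whether total burden fell or whether a stopped drug was replaced from outside the three classes.

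Some stronger readings are tempting, and the documents do not support them:
- **That most of this population exceeds the cut, so the flag is at a ceiling.** Section 2.2 says only that polypharmacy is prevalent. The mean Charlson score of 5.1 in 4.1 measures comorbidity and is not a drug count, and a planned 7+ subgroup gives no prevalence. Nor is a ceiling the mechanism: at mean 6, with 34% below the cut, 86% of one-drug stops still leave the flag unchanged.
- **That dichotomising discards a third to three quarters of the information.** That matches the adjusted efficiencies (1 − 1/1.6 = 38%; 1 − 1/4 = 75%), but only under the assumed distributions and correlations. Without baseline adjustment the same scenarios lose 11% to 41% (efficiency 1.13 to 1.70), and other assumed distributions can bring the unadjusted loss close to zero.
- **That prevalence should be replaced or made merely descriptive.** It is a named endpoint throughout the protocol, Section 3 justifies it by its association with adverse outcomes, and the monitoring board advised on its measurement. Demoting it is a matter of preference; adding the count is not in conflict with it.

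**Conclusion.** The point holds in a limited form. The plan analyses polypharmacy only as a threshold and leaves unused a count that it must compute anyway. That a one-drug change alters status only at the cut follows from the definition; that this concerns 3% to 14% of patients is an assumption-based range. The efficiency gain of 1.6 to 4.0 rests on the assumed count distribution, on one agent removed per stop, and above all on baseline adjustment. The gain is in precision and interpretation on a secondary endpoint. It does not give the trial power for polypharmacy at its design effect, and it leaves the primary analysis untouched. Separately, and without any assumption, the two definitions in 9.4.3 differ: at mean 6 and SD 3, prevalence would be 66% at ≥5 and 52% at >5, and active prescriptions are not the same quantity as agents dispensed over six months.

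**What to change.** In 9.4.3, keep the prevalence endpoint and add:
1. A pre-specified between-arm comparison of the number of different oral agents dispensed in days 91-270, adjusted for the count in the six months before mailing, under the counting rules already given. Name one model in advance, either ANCOVA or negative binomial regression, and report the estimate with its confidence interval.
2. A statement that a null on prevalence will be interpreted from that interval.
3. A table of the observed baseline distribution of the count by arm, including the share exactly at the cut.
4. One definition of the cut and of a counted drug, used identically in the synopsis, Section 3, Section 8.1 and both parts of 9.4.3.

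The cost is one more secondary analysis from data already extracted, plus the text edits; no patients or new data are needed. The change should be dated before outcome data are analysed.
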